While these lifestyle modifications cannot be mandated, participant compliance with these conventions will be strongly encouraged. Per clinical trial evidence linking outcome to dose, all participants will be strongly recommended to be on maximum tolerated doses of a beta blocker and an ACE inhibitor or ARB⁷⁴ to be eligible for entry into the study. Optimal medical therapy was chosen to explicitly test the efficacy and safety of the ICD on top of guideline-driven medical care.

D. Outcome Measures and Rationale

This study is designed to compare the efficacy and safety of ICD implantation in an aged population in reducing all-cause mortality. The primary outcome is measured by survival time. The study is designed to detect 25% reduction in the hazard of all-cause mortality among participants randomized to ICD with an estimated average follow-up of 3.6 years. Key secondary analyses will be quality of life and the effect of ICD in high- versus low co-morbidity burden. Quality of life (QoL) will be measured by the Minnesota Living with Heart Failure

questionnaire, a cardiac disease-specific QoL instrument. Quality of Life will be measured at baseline, six months, twelve months, and twenty-four months.

E. Sample Size

The target sample size for CSP #592 is 1,462 total participants (731 per treatment group to achieve a total of 565 primary outcome events). This sample size will provide 90% power to detect a 25% reduction in hazard from all-cause mortality between ICD + OMT and OMT alone, and will provide ample power to identify clinically meaningful differences between treatments in longer-term safety and Quality of Life measures, as well as significance in the treatment interaction based on co-morbidity burden.

F. Data Collection and Assessments

Study participants will be assessed at baseline via in-person clinic visit and at month 1 to 4 following randomization and every 6 months thereafter via phone-based centralized follow-up; information related to the device will be collected on the day of implantation. The maximum follow-up is 5 years, the average participant follow-up across all participants (recruited in the pilot and full-scale stages) is 3.6 years. Chapter VIII provides details of the baseline assessments and procedures and Chapter 0 describes details of the follow-up schedule and procedures.

G. Alternate Design Considerations

1. Age Eligibility Criterion

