Several different age cut-offs ranging between 65 and 80 years of age were considered for the primary inclusion criterion for this study. The age cutoff of 70 years was selected on the basis that it would yield a population that has not been previously studied well. Importantly, 70 years

is just above the age boundary of the upper quartile of enrollment of many previous clinical trials (See Table 4). Moreover, based on data queries performed within the National Data Service (NDS), and direct communications with investigators from one of these previous trials (SCD-HeFT), a cutoff of 70 years of age is likely to capture the patients for whom the steady decline in utilization of ICD is incipient. An older age cutoff was decided against because it would limit the study's generalizability and could compromise its feasibility due to the increased restriction of the eligible patient pool; whereas, a younger age cutoff, would include many patients where the evidence in support of the efficacy of an ICD is stronger and limit the study's ability to answer the study's primary question, i.e., is ICD implantation safe and effective on top of OMT in reducing mortality in the elderly. We believe that a minimum age of 70 years provides maximum opportunity to extend the extant literature; lowering the minimum enrollment age would dilute the study sample (limiting the study's value in extending the knowledge base), while raising the minimum enrollment age might exclude patients for whom the question of efficacy still appears to exist.

2. Co-morbidities and Functional Status

In addition to age as the primary entry criterion of the study, co-morbidity level and functional status were considered as an eligibility criterion. It is clear that age is an imperfect predictor of mortality risk: a young person with more co-morbid conditions can have a greater mortality risk than an otherwise healthy aged person. Extensive consideration was given to the possibility of including younger patients with co-morbid conditions, but composing a list of conditions or risk level that was clinically meaningful was considered impractical, particularly because of the need to specify for each condition, or combination of conditions, a severity range that would constitute "moderate" risk. A general health status index, e.g., the Charlson Index, was

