Trial safety will be monitored by CSPCC and the CSPCRPCC, and the Study Chair's Office throughout the study. Safety reports will be submitted to the DMC approximately every 6 months after enrollment begins, or more frequently, if requested by the DMC. For reports to the DMC closed session, serious adverse events will be summarized by treatment groups, and relatedness to the assigned interventions.

The proportion of participants experiencing an SAE in each treatment group will be calculated. If the DMC finds the proportion of SAE unacceptably higher in one treatment group compared to another, the DMC may consider recommending that the trial be stopped or that the protocol be modified.

C. Final Statistical Analysis of the Data

All primary analyses will be according to the principle of intent-to-treat; i.e., subjects will be analyzed according to their original treatment assignment regardless of adherence to protocol.

1. Baseline Comparability

Because of the size of this study, we expect that the randomization process will produce reasonably comparable groups of participants. However, the adequacy of the randomization will be assessed by comparing the distribution of baseline demographics, medical history, and clinical characteristics among the treatment groups. Comparability for continuous variables will be examined graphically and by summary statistics (means, medians, quartiles, etc.). Categorical variables will be examined by calculating frequency distributions. Adjustment for significant treatment imbalances in baseline covariates will not be done in the primary analysis because this approach can be biased^{126,127}. Instead, sensitivity analyses examining the treatment effect will be conducted using a model adjusted for a predefined set of important clinical covariates known to moderate or mitigate outcomes. They will include age at randomization, number of previous myocardial infarctions (MI), and baseline left ventricular ejection fraction.

2. Analysis of the Primary Outcome

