The total number of SAE will be summarized by treatment. The proportion of participants experiencing an SAE will be calculated for each treatment group. A chi-square test for the difference in the proportion of SAEs will be used to compare treatment groups over all at the 0.05 level, and with subgroupings of SAEs and non-serious AEs at the 0.01 significance level. Treatment comparisons will be made for the number of participants experiencing SAE, the number of treatment-related SAE, and for the number of non-serious adverse events.

6. Exploratory Analyses

Additionally, data from the Informed Consent Questionnaire will be used for exploratory analysis of the association between perceived and actual participant understanding of the study. ICDs are capable of delivering information related to a wide range of parameters including activity level, heart rate variability and battery and lead status. Descriptive analysis will be used to summarize the ICD device data. The analysis will be limited in scope to three activities:

- Routine assessment of device activations to assess shock events;
- Device interrogation upon death; and

- Analysis of device data at follow-up appointments as is done in standard clinical practice.

These activities contribute substantially to optimal medical therapy.

7. Consenting Rates

Whereas there are no known published data on the willingness of elderly patients to consent into a study of this nature, it is incumbent on CSP#592 to measure and report the rates of consent among patients deemed so eligible. Data collected from patients found eligible for entry into the study will be analyzed for rate of consenting into the study, as well as rationale for non-matriculation. This activity contributes substantially to the knowledge base for the design of future clinical trials both in the study of the elderly, and in device-based trials.

XVI. FEASIBILITY

A. Estimating the Patient Population

1. ICD Candidacy among VA Patients

a) Candidacy Criteria

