2.2.9 Analysis of Safety Data

New Adverse Events (AEs) will be collected for only 30 days post-randomization (OMT arm) or 30 days post-implantation (ICD arm); these events will be followed throughout the study until study close or AE resolution, but new AEs will not be collected after this period. All reportable non-serious and serious adverse events will be coded by one or more AE specialist. The total number of AE/SAE, and total number of participants experiencing an event will be summarized by treatment. The proportion of participants experiencing an AE/SAE will be calculated for each treatment group. A chi-square test for the difference in the proportion of SAEs will be used to compare treatment groups over all at the 0.05 level. Treatment comparisons will be made for the number of participants experiencing SAE, the number of treatment-related SAE, and for the number of non-serious adverse events.

In addition, the adverse events will be summarized according to the Medical dictionary for Regulatory Activities (MedDRA)³⁷, in terms of system organ class and preferred terms, by treatment and as overall (Tables 17 and 20).

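### The ample-power claim for longer-term safety has no calculation behind it, fails at 731 per arm for uncommon harms seen in both arms, and no harm is given an effect estimate or interval

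*Combined protocol and SAP*

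**What the plan says.** Protocol III.E sets the target at 1,462 participants, 731 per arm, and says this number "will provide ample power to identify clinically meaningful differences between treatments in longer-term safety and Quality of Life measures". Safety belongs to the trial's question: the protocol's abstract names safety and efficacy as the overall aim, and III.G.1 puts the question as "is ICD implantation safe and effective on top of OMT in reducing mortality in the elderly". The formal objectives in protocol II contain no safety hypothesis.

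New non-serious AEs are collected only in a 30-day window, while SAEs are collected throughout (protocol XIV.C). Longer-term safety therefore means SAEs.

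On analysis, protocol XV.C.5 plans counts and proportions by arm, a chi-square test of SAEs overall at 0.05, and tests "with subgroupings of SAEs and non-serious AEs at the 0.01 significance level". SAP 2.2.9 keeps only the overall test: "A chi-square test for the difference in the proportion of SAEs will be used to compare treatment groups over all at the 0.05 level". For specific harms it gives descriptive summaries by MedDRA class and preferred term, with no test level. At interim looks the rule is committee judgement (protocol XV.B.5): "If the DMC finds the proportion of SAE unacceptably higher in one treatment group compared to another", it may recommend stopping the trial or changing the protocol.

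**The concern.** An unqualified claim of ample power tells readers that a clinically meaningful excess of harm would probably be seen if it existed. Nothing in either document supports that. Protocol XV.A.3 gives figures for the interaction and for quality of life, and none for safety.

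The overall SAE test does not fill the gap. Death and hospitalization are themselves SAEs (protocol XIV.B.4), and the plan projects cumulative mortality of 42.0% against 34.1%. The overall proportion therefore mixes any survival benefit with any harm. Specific harms have to be read from the component comparisons, and those have the least power and no planned interval. The SAP's shells for mortality outcomes (Tables 24, 25 and 27) carry a hazard ratio with a 95% confidence interval. The AE and SAE summaries (Tables 15 to 20) carry counts and percentages only.

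At stake is how an uncommon harm with no significant difference is described when the trial reports on safety in this age group.

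**Working it through.** **The plan's own figures.** There is no safety power figure to reproduce. The neighbouring figures do reproduce, so the design inputs are understood. For quality of life, 0.73 / (5 × √(2/731)) = 2.791 and Φ(2.791 − 1.960) = 79.7%, against 80% stated. For the primary endpoint, a log-rank calculation with the stated mortality, hazard ratio, crossover and 1% annual loss gives 1,457 patients and 563 events, against 1,462 and 565.

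**Inputs.** n = 731 per arm (protocol III.E); two-sided 0.05 (both documents) and 0.01 (protocol XV.C.5 only). Control rates are assumptions, because the documents give none, so a range is shown.

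**Formula.** With d = p2 − p1 and p̄ the mean rate, SE0 = √(2p̄(1 − p̄)/n), SE1 = √((p1(1 − p1) + p2(1 − p2))/n) and power ≈ Φ((d − z·SE0)/SE1).

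For 2% v 4%: SE0 = √(2 × 0.03 × 0.97/731) = 0.00892; SE1 = √((0.0196 + 0.0384)/731) = 0.00891.
- At 0.05: (0.02 − 1.960 × 0.00892)/0.00891 = 0.28, power 61%.
- At 0.01: (0.02 − 2.576 × 0.00892)/0.00891 = −0.33, power 37%.

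Exact enumeration of the uncorrected Pearson test (summing the two binomial distributions over every table with p below the level) gives:

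| Assumed rates, OMT v ICD + OMT | Power at 0.01 | Power at 0.05 |
|---|---|---|
| 1% v 2% | 15% | 36% |
| 2% v 4% | 36% | 62% |
| 3% v 6% | 58% | 80% |
| 5% v 10% | 86% | 96% |
| 0% v 1% | 60% | 93% |
| 0% v 2% | 99% | >99% |

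A continuity correction lowers the 2% v 4% figures to 31% and 55%.

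**Size needed.** For 80% power at 2% v 4%, the same approximation requires 1,141 per arm at 0.05 or 1,698 at 0.01, against 731 planned.

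**Detectable differences, 80% power, 731 per arm.**
- At 0.05: 2% v 4.6%, or 5% v 8.7%. Check for the first: SE0 = 0.00936, SE1 = 0.00933, (0.0262 − 1.960 × 0.00936)/0.00933 = 0.84, and Φ(0.84) = 80%.
- At 0.01: 2% v 5.4%, or 5% v 9.7%.

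**What a null result would leave open.** If both arms show 2%, the 95% half-width is 1.96 × √(2 × 0.02 × 0.98/731) = 1.44 points. An absolute excess of 1.4 points, about 70% of the control rate, would not be excluded.

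**The case against.** Several stronger readings are tempting, and the documents do not support them.

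- A reader might infer that non-significance will be taken as proof of safety. No passage says so. Protocol XV.A.3 and SAP 2.1 describe all endpoints other than the primary as exploratory.
- A reader might infer that harms are judged only by a p-value at 0.01. That level is in the protocol alone. The data monitoring committee also judges SAE proportions without a numerical boundary, and the tables show counts by arm, attribution and outcome, from which an interval could be derived.
- A reader might infer that a doubled harm would usually be missed. Among the doublings tabulated, that holds at 0.01 for control rates of 2% or less and at 0.05 only for 1%. SAEs accrue over an average of 3.6 years in patients aged 70 or over, so some categories, such as other infections, may be well above 2%.
- The gravest harm is not underpowered. Fatal harm enters the primary endpoint, which has 90% design power and a hazard ratio with an interval. Device-bound harms with almost no events under OMT are readily detected once they reach about 2% in the ICD arm.
- Dropping the 0.01 level has a price. Over the 11 SAE types listed in XII.F, if independent, the chance of at least one false signal is 1 − 0.99^11 = 10% at 0.01 and 1 − 0.95^11 = 43% at 0.05.

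All of this stands, and it limits the point. It does not supply the missing calculation, make the claim true for uncommon two-arm harms, or put an interval in the plan.

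**Conclusion.** The point holds in limited form. The statement in III.E is unsupported, and it is wrong for uncommon harms that occur in both arms: power to detect a doubling is 15% to 58% at 0.01, and 36% to 80% at 0.05, for assumed control rates of 1% to 3%. It is reasonable for harms of 5% or more that double.

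These figures assume that all 731 per arm contribute to a simple proportion. The planned 2.5% annual drop-in from OMT to ICD would dilute a device-related excess and lower them. They depend on control rates that the documents do not give, so the range matters more than any single cell.

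Separately, neither document plans an effect estimate or interval for any harm, and the two disagree on whether specific harms are tested at all. The primary analysis, its sample size and the interim safety arrangements are unaffected. This is a correction of wording and reporting, worth making before the data are analysed.

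**What to change.** 1. **Protocol III.E.** Replace the ample-power statement for longer-term safety with detectable differences under named assumed rates: at 80% power and 0.05, about 2% v 4.6% or 5% v 8.7%. If the 0.01 level is kept, also give about 2% v 5.4% and 5% v 9.7%.
2. **Protocol XV.C.5 and SAP 2.2.9.** For each SAE listed in XII.F, report the risk difference (ICD + OMT minus OMT) with its 95% confidence interval. Base any statement of no excess harm on the upper confidence limit, not on a non-significant test. SAP Tables 18 and 19 have no row for incisional pain, lead dislodgement or lead fracture, which XII.F lists, so those rows need adding.
3. **Reconcile the two documents** on whether the 0.01 level for subgroupings applies. Dropping it is not required; the intervals are useful either way.

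**Cost.** The stated safety power becomes less favourable, and the safety tables need a little more analysis work. No extra patients, visits or data are needed.

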Patients with SHF codes were categorized as a) having no ICD, or b) having ICD, based on the appearance of ICD-9 device code V45.02 anywhere in their medical record. For those with no record of ICD possession, a ‘benchmark’ visit date was taken from the FY2009 medical record; if a patient made multiple visits in FY2009, a representative visit was selected at random from all FY2009 visits (see Section I.C.4). For those with ICD, a surrogate “date of implantation” was estimated according to the date at which the device code first appeared in the medical record following at least one visit with SHF code but no device code. Charlson co-morbidity index score was calculated following interrogation of all medical records in the two years preceding the benchmark (SHF) and surrogate implantation (SHF + ICD) dates.

By computing the Charlson score for both SHF patients without ICD as well as ICD-implanted patients, it is possible to both: ascertain the general health status of the potentially eligible patient pool, as well as to make preliminary inferences as to whether there is a systematic difference between those who are eligible to receive versus those who receive ICD, in terms of co-morbidity burden. Summary results are presented in Table 7.

Table 7. General health status of CSP #592 potentially eligible patient population: Co-morbidity burden of SHF patients (top series), mirror that of patients already in receipt of ICD (bottom series); Source: National Data Service.						
Charlson Score	1	2	3	4	5+	Total
SHF Patients without ICD						
N	316	511	561	616	2,066	4,070
Percentage	7.8%	12.6%	13.8%	15.1%	50.8%	100%
SHF recipients with ICD (on day of ICD receipt)						
N	86	195	264	268	820	1,633
Percentage	5.2%	11.9%	16.2%	16.4%	50.2%	100%

Here, two inferences are made: Firstly, the potentially eligible patient population is, –in general– heavily burdened: All patients have Charlson ≥ 1 ; the majority of patients have Charlson ≥ 5 ; Charlson scores in this higher range are associated with a greatly elevated mortality risk. Secondly, it is evident that there is high concordance between the Charlson score distribution across SHF patients with- and without ICDs: there does not appear to be a systematic difference in general health status between those who receive and those who do not receive and ICD.

F. Implantation Rates by Disease Category

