H. Justification of Stratification at Charlson Index 3

Though general health status does not appear to be associated with the rate of ICD implantation, whether there exists an interaction between co-morbid burden and treatment effect remains to be seen. Accordingly, this study will stratify on the basis disease burden, specifically participants will be stratified into “fair” and “poor” health status, on the basis of their Charlson score being lesser versus greater than/equal to 3. This threshold was established following the database review, and in consideration of the general criteria for implantation. Because those patients with the highest co-morbidity score would likely be determined to be ineligible for study (on the basis of 1-year survivability) we estimated the median Charlson score of study-eligible patients would be closer to Charlson score of 3. In this context, a classification of “fair” health status as corresponding to Charlson score of <3 is well-suited in terms of study feasibility, and would commensurate with the existing body of literature to which this study will ultimately be compared. This stratification is in addition to stratification by site.

VI. OUTCOME MEASURES

A. Primary Outcome

The primary outcome measure for this study will be death from any cause analyzed as time to event. The date of randomization will be used as the time origin. VA Vital Status File will be used to determine the vital status of all study participants who are lost to follow-up at study exit. The VA Vital Status File has been shown to be highly accurate compared to the National Death Index (NDI) ⁸³. As cause of death is not available from the VA Vital Status File, a NDI Plus database search will be performed for all participants who are found to have died through the database search in order to adjudicate the cause of death for secondary outcomes.

B. Secondary Outcomes and Exploratory Analyses

1. Quality of Life

Among the cardiac-specific quality of life (QoL) instruments, the Minnesota Living with Heart Failure questionnaire (MLHF) is considered to be among the best ⁸⁴. It has been widely validated ⁸⁵⁻⁸⁷, and it is more sensitive than the generic QoL measures in detecting clinically important changes over time in patients with heart failure ^{88,89}. The MLHF was also chosen as the QoL measure for this study because it is simple, inexpensive, short, easily understood by ill and elderly individuals, self-administered, and easy to score ⁹⁰⁻⁹⁷.

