Because the VA Vital Status File will be searched for all deaths, loss-to-follow-up for the primary endpoint is considered to be very negligible and was therefore not accounted for in the sample size calculation. Based on a 15% annual event rate in the control arm and a hazard ratio of 0.75, and the other assumptions listed above, a sample size of 1,462 (565 total primary outcome events) will be needed in order to achieve 90% power with a 2-sided Type I error rate of 0.05.

Using the target sample size of 1,462, the following scenarios were considered as sensitivity analyses:

- If the recruitment rate is less than anticipated, the study will still maintain 80% power to detect a hazard ratio of 0.75 with 1,084 participants (422 events).
- If the control group annual event rate was 3% lower than anticipated (i.e. 12% annual mortality rate) the study would still maintain 81.0% power to detect a hazard ratio of 0.75.
- If the effect size is smaller than hypothesized, the study would still maintain 80% power to detect a hazard ratio of 0.78.

3. Power for Secondary Analyses

The secondary objectives for this trial are to test the treatment interactions by co-morbidity level, and to test the change from baseline in the Minnesota Living with Heart Failure score. Neither secondary analysis will require adjustment for type I error, i.e. no “multiple testing” corrections: adjustments for multiple comparisons are required in confirmatory whenever results from multiple tests have to be combined in one final conclusion and decision; in studies with a single primary endpoint, all other endpoints are considered subsidiary and their results can only have an exploratory rather than a confirmatory interpretation – multiplicity corrections are not required¹²⁴. A sample size of 1,462 participants will yield the following power for secondary endpoints:

- Assuming equal enrollment across high- and low-burden groups, this study will reach statistical significance for an increased in therapeutic effect by 50% in the low-burden group (Charlson <3) and decrease in efficacy of 50% in the high-burden group (Charlson ≥ 3). Assuming a pooled standard deviation of 5 for change from baseline in Minnesota Living with heart failure score, the study will have 80% power to detect a 0.73 difference between groups in mean change from baseline at 12 months.

B. Interim Monitoring and Analysis

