2.2 Statistical and Analytical Plans

2.2.1 Randomization Scheme

Veterans who satisfy all of the study eligibility criteria, provide written informed consent and complete the necessary baseline assessments will be randomized to one of two treatment strategies: ICD therapy + optimal medical therapy, or optimal medical therapy alone. The treatment assignment will be provided through a web-based randomization platform or over the telephone to the site investigator or coordinator. The treatment allocation ratio for the two treatment regimens will be 1:1 within each stratum; participants will be stratified both by medical center and by Charlson score (Charlson <3, and Charlson \geq 3), using a random permuted block scheme with randomly varying block size. The random treatment scheme has been generated by CSPCC. When a subject is to be randomized, the Study Coordinator or Local Site Investigator will complete the eligibility and baseline forms. If all eligibility criteria are satisfied and informed consent has been obtained, a new randomization will be assigned. This procedure has been tested and validated before enrollment began.

The CSPCC will review the overall and by-site randomization at least weekly during the enrollment phase of the study, and will be monitoring the randomization transactions with equal or greater frequency. The participant's unique study ID number will be linked in the randomization file to the treatment assignment for each individual. The randomization file data will remain separate from the rest of the study data on the central database.

Randomization may occur on the same day the patient has completed the necessary portions of the Screening and Baseline assessments and is judged eligible for

randomization. Delay in randomization due to participant or medical circumstances are permitted up to a maximum of 30 days past baseline data collection; if randomization is delayed further, baseline data must be collected anew. When a new participant has been enrolled, his/her electronic medical record will be updated indicating participation in the study. Source documentation for eligibility criteria and randomization will be kept at the site with the participant's study folder.

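### The stated significance of the co-morbidity interaction rests on equal enrolment across Charlson 3, but the protocol's own data point to about 20/80 to 30/70, where it is lost

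*Combined protocol and SAP*

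**What the plan says.** - **Protocol V.E, Table 7** is titled "General health status of CSP #592 potentially eligible patient population". It gives counts at scores 1, 2, 3, 4, 5+ and in total. For systolic heart failure (SHF) patients without an ICD the row is "N 316 511 561 616 2,066 4,070". For those with an ICD, scored on the day of receipt, it is "N 86 195 264 268 820 1,633". The text below the table notes that "the majority of patients have Charlson ≥ 5".
- **Protocol V.H** chooses 3 as the cut because "we estimated the median Charlson score of study-eligible patients would be closer to Charlson score of 3". The reason given is that the one-year survival criterion will exclude the highest scorers; no figure is given for how many. Feasibility and comparability with the literature are also cited.
- **Protocol IX.A and SAP 2.2.1** use the cut in randomisation: "participants will be stratified both by medical center and by Charlson score".
- **Protocol XV.A.3** states the expectation for the interaction: "Assuming equal enrollment across high- and low-burden groups", it will be significant for an effect 50% larger below 3 and 50% smaller at 3 or above. The sentence gives no power percentage.
- **Protocol III.E** and the Coordinating Center director's letter both describe the power for co-morbidity differences as ample.
- **Protocol XV.C.3.a and SAP 2.2.6.1** plan the interaction test both at <3 versus ≥3 and with Charlson as a continuous measure.

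**The concern.** V.H and XV.A.3 do not agree with each other or with Table 7. A median of 3 does not produce equal groups at <3 versus ≥3, because patients who score exactly 3 all fall in the upper group. Table 7 in turn puts the median in the 5+ class in both rows. An unequal split costs precision, because the variance of an interaction estimate is driven by the smaller stratum.

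Benefit at high versus low burden is called a particularly important secondary objective in the protocol's summary. If the power statement is wrong, readers will expect the trial to settle a question that it is unlikely to settle, and a non-significant interaction could be taken as evidence of a uniform effect.

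**Working it through.** **Step 1. Table 7 shares.**
- Below 3: (316 + 511)/4,070 = 827/4,070 = 20.3% without ICD; (86 + 195)/1,633 = 281/1,633 = 17.2% with ICD.
- At 3 or above: 79.7% and 82.8%.
- At 5+: 50.8% and 50.2%, as printed, so the median is 5 or more in both rows, by a narrow margin.

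**Step 2. Apply V.H's own argument.** Remove patients from the top of the no-ICD row until the median is 3.
- Scores ≤3 number 316 + 511 + 561 = 1,388, so at most 2 × 1,388 = 2,776 patients can remain.
- That removes 4,070 − 2,776 = 1,294 patients, or 63% of the 2,066 in the 5+ class.
- Below 3 is then 827/2,776 = 29.8%, leaving 70.2% at 3 or above.
- Removing all 5+ patients gives 827/2,004 = 41.3% below 3.
- An equal split needs 2 × 827 = 1,654 patients to remain, so 2,416 (59% of the pool) must go: all 2,066 at 5+ and 350 of the 616 at score 4.
- From the ICD-recipient row, removing all 5+ patients gives 281/813 = 34.6% below 3.

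**Step 3. The interaction.** Inputs: 565 deaths and HR 0.75 (XV.A.2). I read the 50% changes as applying to the 25% hazard reduction: HR = 1 − 0.25 × 1.5 = 0.625 below 3, and 1 − 0.25 × 0.5 = 0.875 at 3 or above. The difference in log HR is ln(0.875/0.625) = 0.336.

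Let s be the share of deaths below 3, taken equal to the share of patients (an assumption). With 1:1 allocation:

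SE = √[4/(565s) + 4/(565(1 − s))], z = 0.336/SE, power ≈ Φ(z − 1.96).

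| Share below 3 | Basis | SE | z | p | Power |
|---|---|---|---|---|---|
| 50% | XV.A.3 | 0.168 | 2.00 | 0.046 | 52% |
| 41.3% | no-ICD row, all 5+ removed | 0.171 | 1.97 | 0.049 | 50% |
| 29.8% | no-ICD row, median brought to 3 | 0.184 | 1.83 | 0.07 | 45% |
| 20.3% | no-ICD row as printed | 0.209 | 1.61 | 0.11 | 36% |
| 17.2% | ICD-recipient row as printed | 0.223 | 1.51 | 0.13 | 33% |

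The 50% row reproduces the protocol's statement, but only in the sense that an observed effect of exactly this size just passes 0.05. As a design property, that is power of about one half.

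If the 50% changes are applied to the log hazard ratio instead (HR 0.650 and 0.866), power is about 40% at 50/50 and 28% at 20.3%, and z at 50/50 is 1.71, so significance is not reached at any split.

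**Step 4. Scale of the shortfall.** Deaths needed for 80% power are 4 × (1.96 + 0.84)²/[0.336² × s(1 − s)]: about 1,110 at 50/50 and about 1,730 at 20/80, against 565 planned.

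**The case against.** The best defence is that Table 7 does not describe participants. It is the pool before the one-year survival exclusion, which is exactly why V.H expects a lower median. It covers SHF-coded patients only, who are 5,723 of 74,673 (7.7%) in the Table 19 recruitment pool; the documents give no Charlson distribution for the rest. The ICD-recipient row looks like a check on the survival argument, since recipients score no lower. But it uses a surrogate implant date and a device code that does not separate primary from secondary prevention. This stands. A reader might infer that 80% of participants will fall in one stratum; the documents support that only for the pool. The tabulated scenarios put the share of participants at 3 or above anywhere from about 59% to 83%. At the 59% end, the significance statement just survives (p = 0.049).

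A reader might also infer that the cut should move to 5, the Table 7 median. That holds only if the survival criterion removes almost nobody. With the median brought to 3, the 5+ class keeps 2,066 − 1,294 = 772 of 2,776 patients, a 72/28 split that is no better than 70/30. SAP 2.2.1 also says that the randomisation scheme has already been generated.

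A third tempting reading is that the cut separates ischaemic from non-ischaemic disease, since a prior MI scores a point. The documents give no MI frequency by score, and V.E scores only the preceding two years of records, so this is not shown.

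Finally, the secondary analyses are declared exploratory, and the continuous-Charlson test is already planned. Both limit the consequence; neither makes the stated power correct.

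**Conclusion.** The equal-enrolment assumption is contradicted by the protocol's own figures, whether Table 7 is taken as it stands (about 20/80) or adjusted to V.H's expected median (about 30/70). At those splits the interaction described in XV.A.3 gives p of about 0.11 and 0.07, with power of about 36% and 45%. Even at 50/50 power is about 52%, so calling it ample is unsupported.

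This rests on three assumptions: deaths divide in proportion to patients, the survival criterion removes patients from the top of the score range, and the 50% changes apply to the hazard reduction. The first favours the low stratum, since V.E links high scores to higher mortality. The log-scale reading of the third gives lower power still.

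The primary stratified test is not biased by unequal strata, and the choice of 3 as a stratum is not itself shown to be wrong. The error is confined to the secondary power claim and the wording that depends on it.

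**What to change.** 1. In Protocol XV.A.3, replace the equal-enrolment assumption with a split of 20/80 to 30/70 and state power rather than significance: with 565 deaths in proportion to patients and HR 0.625 versus 0.875, power is about 36% to 45%. State the scale on which the 50% changes apply.
2. Remove the ample-power wording for co-morbidity from Protocol III.E and from the Coordinating Center director's letter.
3. Keep Charlson 3 as the randomisation stratum.
4. In Protocol XV.C.3.a and SAP 2.2.6.1, name the already planned continuous-Charlson interaction as the main burden test, with <3 versus ≥3 as supportive. No alternative cut need be prescribed.

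The cost is wording only; no new data or allocation lists are needed. The downsides are a less favourable stated power for a secondary objective, and reliance on the continuous test's assumption that the log hazard ratio changes linearly with the score. The power of that test cannot be derived from Table 7, because the 5+ class is open-ended.
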